 - drug group x session interaction ($p<0.05$) followed by MEM+TCT > PBO+TCT at specific session # or combination;
4. **More durable** clinical, neurocognitive **or** functional gains:
 - MEM+TCT > PBO+TCT at post-TCT week 12.

PANSSt: *Positive & Negative Symptom Scale total*; MCCB-C: *MATRICS Composite*; Fnxn: *Function (assessed via the World Health Organization Disability Schedule 2.0 (WHODAS))*

Rhythm Recall: Subjects listen to and replicate a short rhythmic sequence. This task is designed to stimulate both basic auditory processes supported by primary auditory cortex, and non-verbal auditory WM.

Symptoms are assessed to track clinical status and TCT response. TCT reduces positive symptoms of psychosis, and we predict that MEM will augment these effects via enhanced TCT learning (i.e. not via a lasting direct pharmacological effect of MEM), detected by the Positive & Negative Syndrome Scale. For this reason, and based on the need to limit total outcome measures, **PANSS Total Score is the primary clinical outcome measure**. Positive and negative symptom subscales, as well as PANSS factor-derived measures, will be assessed in exploratory analyses. Other secondary clinical measures will include: 1) Psychotic Symptom Rating Scales (PSRS; assesses auditory hallucinations); 2) Young Mania Rating Scale; 3) Patient Health Questionnaire-9 (PHQ-9; current depressive symptoms); 4) Abnormal Involuntary Movement Scale (AIMS); 5) **C-SSRS**; “Lifetime/Recent version” at screen; “Since Last Visit” at follow-up visits). The C-SSRS is a reliable, valid and sensitive measure of suicidal ideation⁹⁸; *any “yes” in C-SSRS prompts an immediate full evaluation/action plan by a study M.D.; and* 7) MEM Cessation Symptom Assessment (ACSA).

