Post-treatment protocol: On completion of 30 TCT sessions, participants will be offered the option of maintaining their assigned drug (PBO or MEM) through the 22-week durability assessments. Those who opt to discontinue the study drug will titrate off, over a 3-week period. After week 22, study blind will be broken, and subjects who continued to receive MEM will again be offered the option of titrating off of MEM vs. maintaining MEM treatment coordinated with, and under the supervision of, their primary provider.

Data Analysis: “Go/No Go” decisions are based on traditional statistical significance (Aim 1) and effect sizes (Aim 2). Formal statistical testing is conducted using linear mixed-effects (LME) models; hypothesis tests are 2-sided ($\alpha=.05$). Model parameters are estimated via the R lme4 package and Cohen’s d is estimated via the

EMAtools package. Type I errors are minimized by constraining the number of primary analyses; secondary analyses use false discovery rate corrections. Expected attrition rates are described above. Because outcome measures involve a “change from baseline”, baseline metrics are compared between PBO and MEM arms, and any baseline differences are addressed in the outcome analyses. Differential drop-out rates from PBO vs. MEM arms are monitored. Data are assumed to be missing at random; full information maximum likelihood estimators are used, and all data/cases are included in analyses. Clinical follow-up is pursued with all patients exiting the study through post-TCT week 12. Cohort differences: For between-subject contrasts (main effect of drug), differences in age, antipsychotic and anticholinergic loads are tested and used as covariates^{2,33,95}. Sex differences are tested for all measures. NIH Data Harmonization: 3 “PhenX Toolkit” (NOT-MH-15-009) measures of function are used; see above and “Resource Sharing Plan”.

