Aim 1 – Confirm target engagement: The primary dependent measure of target engagement is MEM-enhanced APS learning. APS learning is defined as the reduction in Sound Sweeps APS threshold (ms) Test 1 to Test 2 assessment. Target engagement was demonstrated in Fig. 3⁷⁶, and will be confirmed if APS learning is increased by MEM (note that MEM and PBO groups are matched by Test 1 PBO performance via stratified randomized assignment). As appropriate, effect sizes and inferential statistics are based on standard regression or LME models with random intercepts. A significant interaction between contrast coded drug (PBO vs. MEM) and Test (Test 1 vs. Test 2) predictors on APS learning is a “Go” criteria and confirms target engagement.

Aim 2 – Test clinical, neurocognitive and functional impact of MEM on TCT, and its relationship to target engagement: We will determine if MEM+TCT produces greater, faster or more durable clinical, neurocognitive or functional gains from baseline, compared to PBO+TCT, over a 30-session course of TCT. A Cohen’s $d > 0.5$ for the main effect of drug (PBO vs. MEM) or drug x session (#10, 20, 30) interaction in an LME model is the primary “Go” criteria. The effect of drug assesses “greater” gains. Reverse Helmert contrasts for session assesses “faster” gains. A separate model comparing differences in outcomes at 12-weeks post-TCT assesses “more durable” gains. Secondary analyses will examine whether change in MEM-enhanced APS learning (“within-subject” target engagement; Aim 1) predicts gains in Aim 2 outcome measures.

Aim 3 – Biomarkers of MEM-induced gains: We will determine if baseline levels of specific neurocognitive or EEG-based measures, or changes in specific measures with initial MEM exposure (Test 2 vs. 1), predict greater sensitivity to MEM-enhanced neurocognitive, clinical or functional gains over 30-h of TCT. Regression analyses will assess whether specific candidate biomarkers predict MEM-enhanced gains in outcome measures.

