Differential drop-out rates from PBO vs. MEM arms are monitored. Clinical follow-up is pursued with all patients exiting the study through post-TCT week 12.

Cohort differences: For between-subject contrasts (drug), baseline demographic, clinical, antipsychotic/anticholinergic load and performance differences are tested and used as covariates if indicated. Sex differences are tested for all measures.

Procedures for Alternative or Unexpected Results: Linear mixed-effects models allow for the analysis of all available data using an intent-to-treat approach. This approach, however, assumes that data are missing at random. A potential concern is nonrandom dropout, particularly when dropout is related to the (missing) outcomes; that is, not missing at random. To make the missing at random assumption more plausible, we will explore the use of auxiliary variables. Auxiliary variables are covariates that predict both dropout and outcomes. By adding

auxiliary variables to our models, nonrandom dropout is corrected by conditioning treatment effects on the predictors of dropout.

Primary Efficacy Endpoint(s): Aim 1: Target engagement – APS learning will be significantly greater under MEM vs. PBO conditions. Aim 2: Pilot trial - Compared to PBO arm patients, MEM arm patients will exhibit greater clinical benefit, as indicated by one or more of the following: greater, faster or more durable improvements in PANSSt (reduced scores; see below, "Go/No-Go"), MCCBc (increased scores) or WHODAS (reduced scores).

Secondary Efficacy Endpoint(s): Aim 3: Biomarkers - baseline levels of specific neurocognitive or EEG-based measures, or changes in specific measures with initial MEM exposure, predict greater sensitivity to MEM-enhanced neurocognitive, clinical or functional gains over 30 sessions of TCT.

Analyses testing primary and secondary hypotheses will include all subjects' clinical, neurocognitive and functional assessments. Data from subjects who do not complete the full study are carried forward in an "intent to treat" design, and their data are analyzed using linear mixed models. Separate analyses will compare completion / drop-out rates across arms, as well as a 14-item 7-point Likert scale assessing treatment satisfaction.

Go/No-Go decision and primary and secondary endpoints

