"Go/No-Go" decisions are based on traditional statistical significance (Aim 1) and effect sizes (Aim 2). Formal statistical testing is conducted using linear mixed-effects (LME) models; hypothesis tests are 2-sided ($\alpha=0.05$). Model parameters are estimated via the R lme4 package and Cohen's d is estimated via the EMAtools package. Type I errors are minimized by constraining the number of primary analyses; secondary analyses use false discovery rate corrections.

PANSSt scores will be assessed at specific intervals. Because TCT is associated with improvements in both positive and negative symptoms, our *a priori* hypothesis is that a PACT effect will be evident in both positive and negative symptoms. Hence, PANSSt is used as the primary metric of symptomatic gains. A greater reduction in PANSSt score will be detected using data from baseline through TCT 30h, by a significant main effect of group (arm) or a significant interaction of group x session, with post-hoc contrasts revealing significant group differences at TCT 30h. A faster reduction in PANSSt scores will be detected using these same data by a significant interaction of group x session and a significant group difference at a point prior to TCT 30h. A more durable reduction in PANSSt scores will be detected using data from TCT 30h through 12 weeks post-TCT, by a significant main effect of arm or a significant interaction of group x post-TCT day, with post-hoc contrasts revealing significant group differences 12 weeks post-TCT.

Comparable analytic approaches will be used for neurocognition (MCCBc) and function (WHODAS) as described in "Research Strategy". Data will be described as means with SEM. Tests for normalcy will be applied to all data and non-parametric comparisons will be used if normalcy is not demonstrated. The Analysis Set for these data will be all subjects who have completed 30h of TCT and post-TCT clinical, neurocognitive and function assessments. When appropriate, missing data are handled via multiple imputation or full information maximum likelihood estimation.

Secondary regression analyses assess the predictive value of putative biomarkers on clinical, neurocognitive or functional gains from the addition of MEM to TCT. Future studies with larger samples will assess potentially more informative models, e.g. Path Analysis to study moderating effects of APS MEM sensitivity and biomarkers on both indirect (moderated-mediation) and direct paths between treatment and outcome.

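### A normality pre-test on all data switches outcomes to unspecified non-parametric comparisons, leaving the model-based Go criteria undefined for any outcome that fails it

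*Combined protocol and SAP*

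**What the plan says.** Under the Go/No-Go heading of section 4.4: "Tests for normalcy will be applied to all data and non-parametric comparisons will be used if normalcy is not demonstrated". The normality test, its level, the quantity tested (raw score, change or residual) and the non-parametric method are not named.

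The rest of the plan is built on models:

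- **Primary method** (section 4.4, same heading): "Formal statistical testing is conducted using linear mixed-effects (LME) models; hypothesis tests are 2-sided". Parameters come from lme4, and Cohen's "d is estimated via the EMAtools package".
- **Aim 1 Go** (Research Strategy, Data Analysis): a significant drug x Test interaction from standard regression or an LME with random intercepts.
- **Aim 2 Go** (same place): Cohen's d must exceed 0.5, and the text attaches this threshold to model terms: "for the main effect of drug (PBO vs. MEM) or drug x session (#10, 20, 30) interaction in an LME model is the primary" (the sentence ends by naming it a Go criterion).
- **Faster gains** (Table 1): "drug group x session interaction ($p<0.05$) followed by MEM+TCT > PBO+TCT at specific session # or combination".
- **Missing data** (Research Strategy, Data Analysis): "full information maximum likelihood estimators are used, and all data/cases are included in analyses". Section 4.4 says that, when appropriate, "missing data are handled via multiple imputation or full information maximum likelihood estimation". Its paragraph on alternative or unexpected results gives the rationale: "Linear mixed-effects models allow for the analysis of all available data using an intent-to-treat approach".

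**The concern.** The rule tests the wrong thing. An LME needs approximately normal residuals; it does not need normal raw scores, and the rule covers all data. A test that does not reject also does not demonstrate normality, least of all in a small sample.

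The larger problem is what follows a failed test. The outcome leaves the model that defines its Go criterion, and the plan supplies nothing in its place. An ordinary two-group rank comparison yields no Cohen's d, no drug x session or drug x Test interaction, and no likelihood-based use of incomplete records. The last matters because the throughput paragraph expects, conservatively, 18 TCT completers per arm out of 27.

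At stake is the Go decision itself. For a failing outcome, the analyst would have to choose a method and a threshold after looking at the data. Aim 1 is exposed as well as Aim 2, since its criterion is a p-value from a model interaction.

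**Working it through.** **1. The plan's own figure.** Inputs from Power analyses: d=0.5, 80% power, two-sided alpha 0.05, test-retest correlation r=0.8, 27 per group. For a pre-post change, the variance in units of the raw SD is 2(1−0.8)=0.4. Then n = 2 × 0.4 × (1.960+0.842)² / 0.5² = 25.1, so 26 per group. Exact t power is 79.8% at 26 and 81.3% at 27. The stated 27 reproduces, so the point does not rest on the sample size.

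**2. Where each Go route stands after a switch.**

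| Go route | Defined on | Counterpart stated for a failed normality test |
|---|---|---|
| Aim 1 target engagement | drug x Test interaction, p<0.05 | none |
| Aim 2 greater gains | model-based d > 0.5 | none |
| Aim 2 faster gains | drug x session interaction, p<0.05, then d | none |
| Aim 2 more durable gains | separate 12-week model, d > 0.5 | none |

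**3. False triggers with exactly normal data.** Assume each test is at 5% and the tests are independent. The chance of at least one rejection in k tests is 1 − 0.95^k.

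- k=3 (PANSS total, MCCB composite and WHODAS, once each): 14.3%.
- k=4 (adding APS learning): 18.5%.
- k=17 (three outcomes at baseline, sessions 10, 20, 30 and 12 weeks post-TCT, i.e. 3 × 5 = 15, plus APS learning at Tests 1 and 2): 58.2%.

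Repeated scores in the same patients are correlated, so these are roughly upper bounds for each k. The documents do not say which k applies.

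**4. Triggers with skewed data.** Simulated lognormal data, 4,000 runs, Shapiro-Wilk at 5%. The test and the shapes are assumptions. Log-SD 0.25 gives skewness 0.78, and log-SD 0.4 gives 1.32.

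- n=54: 46% and 83% rejected.
- n=36 (18 per arm): about 32% and 62%.

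The APS threshold is in milliseconds, so it is positive and plausibly right-skewed.

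**5. Power at d=0.5, r=0.8, normal data.** The residual SD with baseline adjustment is √(1−0.64)=0.6, the change SD is √0.4=0.632, and the end-score SD is 1. The first two columns and the end-score t test are exact; the rank columns are simulated.

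| Per arm | Baseline-adjusted | t on change | Rank on change | Rank on end score |
|---|---|---|---|---|
| 27 | 85% | 81% | 79% | 42% |
| 18 | 68% | 63% | about 60% | about 28% |

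Ranking change scores costs 2 to 4 points against a t test on change. At r=0.5 and 18 per arm the pair is 31% and 29%. The fall to 42% comes from ignoring baseline: a t test on end scores at 27 per arm has only 44%. With skewed data (log-SD 0.5, r=0.8) ranks on change gain: 88% against 79% at 27 per arm, and 70% against 62% at 18.

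**The case against.** The strongest reply is that the sentence speaks only of comparisons. It comes after a description of post-hoc group contrasts, in a section that opens by basing the Aim 2 decision on effect sizes. On that reading the LME-based d still decides Go, and only the significance tests change. This is reasonable, but no text states it, and it would not rescue Aim 1 or the faster route, which depend on p-values for model interactions. What stands is that the d rule is left undefined. A reader might infer that the plan abandons the mixed model and the d rule outright; the documents do not say so.

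A reader might also infer three further things that the documents or the numbers do not support.

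- **That switching loses power in general.** It does not. The cost with normal data is small, and ranks can gain where skew makes the switch likely. A large loss needs a rank test on end scores, and the plan frames its outcomes as change from baseline.
- **That missing-data handling disappears.** Only the likelihood route goes. Multiple imputation is also named and could accompany a rank test, though nothing links the two. Rank methods for covariates and repeated measures exist; the plan names none.
- **That the switch is what costs the analysis of all randomised patients.** Section 4.4 already limits the Analysis Set to those completing 30 h of TCT and the post-TCT assessments. That conflicts with the intent-to-treat text whether or not the switch fires, and is a separate matter.

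The 58% figure requires 17 independent tests that the documents do not specify. It is also the chance that some dataset fails, which is not the chance that a Go decision changes.

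**Conclusion.** The concern holds as a fault in the rule. An unspecified, data-dependent switch takes any failing outcome away from the model that defines its Go criterion, and no replacement criterion is given.

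The trigger is not remote: about 14–19% for at least one false trigger if each outcome is tested once, up to 58% if every outcome is tested at every visit, and about 46–83% per dataset of 54 at skewness of roughly 0.8 to 1.3. These figures rest on a 5% Shapiro-Wilk-type test, independence between tests (first two figures) and lognormal shapes (the last). None of these comes from the documents.

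The harm is structural. The one large power cost, from about 85% to 42% at 27 per arm, arises only if the unnamed rank test ignores baseline. The text neither requires nor excludes that. The point should be settled before unblinding because it bears directly on Go.

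**What to change.** Replace the sentence in section 4.4 with the following:

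- The regression or LME model, with its d, is the sole Go analysis for Aims 1 and 2 for every outcome, whatever the distribution.
- Assumptions are checked on model residuals. There is no pre-test of raw data.
- Any transformation, for example the log of the APS threshold, is fixed before unblinding, together with the scale on which d is reported.
- A bootstrap or robust-standard-error interval for the same contrast, and a rank test that uses baseline, are reported as sensitivity analyses and do not alter Go.

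The cost is a wording change and slightly more analysis work, with no extra patients or visits. The change does not resolve the completer Analysis Set, which needs its own correction.

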Fig. 5. Study Phases: Baseline & Randomization includes 2 Sound Sweeps tests: Test 1 with PBO and \approx 5-7 days later Test 2 with either MEM or PBO. Treatment Phase includes 30 TCT sessions with outcome measures after 10, 20 and 30 sessions. Post-treatment tests assess both immediate biomarker changes and 12-week durability of outcome gains.

Assessments: 30 sessions of TCT will be completed, based on our findings (Fig. 1) and evidence that TCT efficacy is dose-dependent^{25,68,97}. Assessment dates could be based on either: 1. session # (10, 20 and 30 and 12 weeks later); or 2. Time (days) since starting TCT. In our experience^{2,31,34} TCT rates closely match 3/week (30 sessions mean = 65 days; 90% of subjects completed 30 TCT sessions within 11 weeks). Primary analyses will be based on session #, but session dates are recorded and confirmatory analyses will define assessment points based on time passage. Candidate predictive biomarkers are re-tested after session 30.

General Clinical Monitoring: In addition to their established ongoing care, patients are carefully monitored at each session as per our well-established procedures, and through to the week-22 follow-up, for any clinical changes. Each week, a member of our research staff checks vital signs and weight, does a detailed assessment of symptom changes, focusing on psychosis, depression, suicidality and abnormal movements, and tests UTox and pregnancy. A designated unblinded staff member processes UTox results. In the event that a subject tests positive for recreational drugs or a positive pregnancy test, it is promptly reviewed with the on-site Psychiatrist; any “yes” on the Columbia Suicide Severity Rating Scale⁹⁸ (C-SSRS) “Since Last Visit”, or an exacerbation of psychotic symptoms, prompts detailed review, with appropriate clinical interventions. Patients testing positive for recreational drugs will be retested in 1 week; patients with 3 positive tests no longer continue in the study. **Data from subjects who, for this or other reasons, do not complete the full study are carried forward in an “intent to treat” design, and their data are analyzed using linear mixed-effects models.**

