Staff assessing outcome measures are blind to treatment arm, and for some measures receive training using videotaped and practice interviews until achieving high (ICC>.80) reliability based on 20 assessments by 2 raters. We achieve high inter-rater reliability (e.g., ICC>0.85 for PANSS total), and check for rater drift each 90d.

Specific Procedures: TCT is completed with a dedicated room and equipment. Staff trained with a UCSD-developed “TCT Clinician Competence Assessment” monitor TCT, clarify instructions and provide encouragement as needed. **In the initial “biomarker testing” session (Test 1),** subjects complete 1-h of Sound Sweeps to generate a “Pre-Training APS score” as described previously (Fig. 3) under identical circumstances and timelines as for the Test 2 session described below. Treatment group assignment (PBO vs. MEM) is then made using stratified random sampling (above) and 5-7 days later patients ingest either PBO (n=27) or 20 mg MEM (n=27) 240 min before completing the Sound Sweeps session (“Test 2”). MEM effects on APS learning are assessed both within-subject (APS (Test 1 - Test 2) for MEM group subjects: a key measure of **MEM sensitivity**) and between subjects (APS Test 2, PBO vs. MEM groups). After Test 2, all subjects are prescribed daily PBO or MEM using a standard titration schedule (MEM 5 mg at hs→ 5 mg bid→ 5 mg am/10 mg hs→ 10 mg bid over 3 weeks). Participants return to the laboratory to complete 1h TCT per our established procedures^{2,34}, which includes 5 modules of auditory/verbal processing exercises. Each module increases in difficulty as performance improves: **1) Sound Sweeps; 2) Syllable Identification:** Patients distinguish between 2 similar phonemes (e.g., “ba” vs. “da”), differing only in their voice onset time; **3) Word Matching:** Subjects match short similar-sounding consonant-vowel-consonant words (e.g., bad, dad); **4) Listen & Do:** Subjects reconstruct a spoken series of instructions and use a computer mouse to click icons on the screen in a specified order. This exercise is designed to stimulate verbal WM processes supported by the lateral PFC as well as premotor and motor processes. **5)**

Table 1. “Go” criteria: #1, plus at least one of #'s 2, 3 & 4 ($d>0.5$)

1. **Target engagement:** APS learning, MEM > PBO, p<0.05
2. **Greater** clinical, neurocognitive **or** functional gains:
 - ↓PANSSt, ↑MCCB-C **or** ↑Fnxn: MEM+TCT > PBO+TCT
3. **Faster** clinical, neurocognitive **or** functional gains:

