Subject “throughput”: We will enroll and screen 23 subjects/yr, test target engagement in 18 subjects/yr, and (conservatively) complete TCT training in 12 subjects/yr. This will yield 2 “target engagement” Aim 1 arms of n=27, and (conservatively) 2 TCT completion Aim 2 arms of n=18. Training capacity (2 TCT stations with morning and afternoon sessions on M, W and F, with T and Th “make-up” days for missed appointments, 48 weeks/year) allows for a “maximum throughput” of 19.2 subjects/yr. To reach the target of **12 TCT-completing subjects/year**, we would need to maintain training rates of **62.5% capacity**. This is well within our historical testing levels.

Power analyses: Consistent with the FOA, this study will adequately power tests of target engagement (Aim 1) for traditional significance, while the “Go” signal for therapeutic impact (Aim 2) is based on effect size ($d=0.5$). To detect target engagement for an LME model with $d=0.5$, 80% power, alpha=0.05, test-retest correlation=0.8, and a linear treatment effect, n=27 randomized participants are required per Hedeker et al (1999). This is a conservative estimate of d for target engagement, since empirically, d for target engagement with 20 mg MEM was 0.85 (Fig. 3). A future Confirmatory Efficacy trial will be powered to apply more robust approaches to Aim 2, e.g. Path Analysis⁶⁰ to study moderating effects of APS MEM sensitivity and biomarkers on both indirect (moderated-mediation) and direct paths between treatment and outcome.

Innovative ideas raise questions. Here are some answers:

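### The sentence that defines the Aim 2 analysis set keeps only TCT completers, while the rest of the plan keeps all subjects under intent to treat

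*Combined protocol and SAP*

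**What the plan says.** Section 4.4, under the Go/No-Go decision and endpoints heading, describes how PANSS total is tested for greater, faster and more durable change and extends the approach to MCCB composite and WHODAS. It then says: "The Analysis Set for these data will be all subjects who have completed 30h of TCT and post-TCT clinical, neurocognitive and function assessments". The next sentence allows multiple imputation or full information maximum likelihood for missing data.

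Four other statements point the other way:

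- Research Strategy, General Clinical Monitoring: subjects who "do not complete the full study are carried forward in an" intent-to-treat design, "and their data are analyzed using linear mixed-effects models".
- Research Strategy, Data Analysis: data are assumed missing at random, "full information maximum likelihood estimators are used, and all data/cases are included in analyses".
- Section 4.4, after the secondary endpoints: analyses of primary and secondary hypotheses take in every subject's clinical, neurocognitive and functional assessments.
- The same paragraph of section 4.4 repeats the intent-to-treat rule for non-completers.

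Section 4.4 (Procedures for Alternative or Unexpected Results) also justifies mixed models by their use of all available data. It discusses non-random dropout and proposes auxiliary variables to deal with it.

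**The concern.** A patient who stops after session 20 is in the Aim 2 analysis under one rule and out of it under the other. The restrictive sentence is the only one that uses the term Analysis Set. It stands among the inferential rules for the primary outcomes, and no text calls it a per-protocol or sensitivity set. An analyst could follow either rule and claim to have kept to the plan, and could make that choice after seeing results.

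The Aim 2 Go decision rests on a point estimate of d against 0.5, so the analysed population bears directly on it. Arms are assigned after Test 1, before TCT starts, so completing 30 hours is a post-randomisation event. Selecting on it gives up the protection of randomisation and bypasses the plan's own provision for dropout. It also discards session 10 and 20 data already collected from later dropouts. That matters most for the faster criterion, which section 4.4 tests at a point before 30 hours.

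**Working it through.** **Can the statements be reconciled?**

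1. Suppose the sentence covers only the means, SEMs and normality checks mentioned just before it. The text does not say so, and the descriptive summaries would then describe a different population from the models.
2. Suppose the imputation/likelihood sentence repairs it. That could fill a missed session 10 or 20 visit in a completer. It does not bring back a patient who is outside the set.
3. A concrete case: under General Clinical Monitoring, "patients with 3 positive tests no longer continue in the study". If this happens before the post-TCT assessments, one rule keeps the patient's data and the other removes them. A later stop need not trigger the conflict.

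**The plan's own counts** (Research Strategy, Subject throughput, over three years)

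- Tested for target engagement: 18 x 3 = 54, or 27 per arm.
- TCT completers, cautious projection: 12 x 3 = 36, or 18 per arm.
- Excluded under the completer rule: (54 - 36)/54 = 18/54 = 33%. The rule also requires post-TCT assessments, so it could exclude slightly more at that completion rate.

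**Data discarded.** Assume 9 dropouts per arm, 3 each last seen at baseline, session 10 and session 20. Patients observed per arm are then 24 at session 10, 21 at session 20 and 18 at session 30. Per outcome and over both arms, the completer rule discards 2 x 6 = 12 of 48 session-10 assessments and 2 x 3 = 6 of 42 session-20 assessments.

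**Precision.** The figure is the ratio of standard errors, completers only over all available data, under compound symmetry. Change scores then correlate at 0.5 whatever the within-patient correlation r. With n10, n20 and n30 patients per arm at the three sessions, in units of the change-score variance:

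- Session 10, change scores: ratio = sqrt(24/18) = 1.155.
- Session 30, change scores: all-data variance = (2/3)/n30 + (1/12)/n20 + (1/4)/n10 = 0.03704 + 0.00397 + 0.01042 = 0.05142. Completers only: 1/18 = 0.05556. Ratio = sqrt(0.05556/0.05142) = 1.039.
- With baseline modelled as an outcome, information is summed over dropout patterns in the same way, for r = 0.5 and r = 0.8.

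| Dropout timing (9 per arm) | Session 10 | Session 30 |
|---|---|---|
| Even: change scores | 1.155 | 1.039 |
| Even: baseline as outcome, r = 0.5 / 0.8 | 1.171 / 1.161 | 1.060 / 1.047 |
| All before session 10 (both models) | 1.00-1.04 | 1.00-1.04 |
| All after session 20 (both models) | 1.22 | 1.06-1.07 |

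For the mean of sessions 10 to 30 under the even pattern, the ratio is 1.12-1.15.

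**What the completer estimate would mean.** If the excluded third of each arm has effect x and completers have d = 0.5, the all-randomised effect is 0.5 x 2/3 + x/3. For x = 0.25 this is 0.42; for x = 0 it is 0.33; for x = 0.75 it is 0.58. The values of x are assumptions. They show only that the two populations can fall on different sides of, or at different distances from, the Go threshold.

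**The case against.** The strongest reply is that the plan's intention is clear. Four statements favour all subjects, and the provisions for missing-at-random data and auxiliary variables would have little purpose in a completer analysis. One loosely placed sentence in a pilot study should not outweigh that. Most of this stands: a reader might infer that Aim 2 is designed as a completer analysis, and the documents as a whole do not support that. What remains is that the sentence is explicit, is attached to the primary outcomes and is qualified nowhere.

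The 33% also rests on a projection that the plan calls conservative. The Assessments paragraph reports that 90% of earlier subjects finished 30 sessions within 11 weeks. If that applied to all who start, about 5 of 54 would be excluded; the documents do not say whether its denominator includes dropouts.

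Other inferences go too far:

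- **A loss of 33 of 69 (48%).** The 69 are enrolled and screened subjects. The design and power text point to 27 randomised per arm, so 54 is the supported base.
- **A doubled chance of a false Go.** Comparing 27 with 18 fully observed patients per arm, the chance of an observed d of at least 0.5 under no effect is 3.6% against 7.1%. But dropouts have no session 30 data under either rule. With the 1.04-1.06 inflation above, the session 30 contrast is roughly 6% against 7.1%.
- **No bias if dropout is equal in both arms.** Equal selection does not make completers represent all randomised patients if the drug effect differs between completers and dropouts, and the plan expects response to vary.
- **The durability model needs the same correction.** It is a different question, about model inputs. The Aim 2 text says "A separate model comparing differences in outcomes at 12-weeks post-TCT assesses" durability, while section 4.4 uses data from 30 hours onward. Those two passages need reconciling first, and the 12-week point is undefined for someone who never finishes TCT.

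**Conclusion.** Wrong as written. The analysis-set sentence in section 4.4 contradicts the intent-to-treat and all-cases statements in the same section and in the Research Strategy, and nothing in the documents resolves the conflict.

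The consequences apply only if the completer sentence is followed. About 18 of 54 patients (33%) would then be excluded after randomisation, on the plan's cautious projection. The estimate would differ from the all-randomised effect if selection differs by arm or if the drug effect differs between completers and dropouts; neither the direction nor the size can be derived from the documents. The precision cost is modest and rests on assumed dropout timing and compound symmetry: 1.04-1.06 at session 30 and 1.15-1.17 at session 10 for even dropout, 1.00-1.22 across timings.

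A mixed model on all randomised patients relies on missing at random, so it reduces this selection problem without guaranteeing its removal, as section 4.4 itself recognises.

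**What to change.** Replace the analysis-set sentence in section 4.4 with:

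> The primary analysis set for Aim 2 is all randomised participants, analysed as randomised, using all available data in the linear mixed-effects models; an analysis of participants who completed 30h of TCT and post-TCT assessments is a sensitivity analysis only.

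In General Clinical Monitoring and in the matching paragraph of section 4.4, change *carried forward* to *retained*. Both places pair the phrase with mixed models, but it could be misread as last observation carried forward.

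The cost is one replaced sentence and one clarified term in two places. No patients, visits or data are added, and the rule adopted is the one that most of the plan already states. The change should be made before unblinding.
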